12.13 Clinician Administered Dissociative States Scale (CADSS)

Descriptive statistics for CADSS total score at baseline and changes from baseline at each assessment time point will be presented by treatment group and cohort.

A listing of CADSS data for all subjects will be provided.

12.14 Modified Observer's Assessment of Alertness/Sediation Scale (MOAAS)

Descriptive statistics for MOAAS total score not equal to 5 will be presented by treatment group and cohort.

A listing of MOASS data for all subjects as described above will be provided.

13. Appendix

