#### Table 1: SAD schedule of assessments and procedures

An early termination visit will be scheduled on an ad hoc basis for any subject who withdraws from the study. \* Physical examinations can be conducted at any additional time at the judgement of the Principal Investigator (eg, to evaluate an adverse event)

^FSH for postmenopausal women at screening visit

\*\* Day 1 Timepoints: 1-hr preinfusion, and 1, 2, 4, 8, and 12 hr after the start of the infusion.

\*\*\* Ocular examinations include visual acuity and color vision tests.

\*\*\*\* On Day 1, MOAA/S is performed preinfusion, during the infusion at approximately 20 min after start of infusion, 40 min after start of infusion, and approximately 1 hr after the start of the infusion.

\*\*\*\*\* On Day 1, CADSS is performed preinfusion and approximately 40 min and 80 min after the start of the infusion.

Procedure	Screening					Confin	ement					Follo	ow-Up
	(Day -28 to Day -2)	Day -1	Day 1	Day 2	Day 4	Day 5	Day 7	Day 8	Day 9	Day 11	Day 12	Day 15	Day 17-19
Informed Consent	X												
Eligibility Criteria	X	X											
Demographics	X												
Height	X												
Weight, BMI	X	X									Х		
Medical history	X	X									Χ	X	X
Physical Examination*	X	X					Χ				Χ		
Vital Signs**	X	X	Х		X	X	X	X	X	X	X		
ECG**	X	X	Х		X	X	X	X	X	X	X		
Urine Drug Test	X	X					X						
Alcohol Breath Test	X	X					X						
Pregnancy Test	X	X					X						
(Females)^													
Serology (Hepatitis C,	X												
Hepatitis B, HIV)													
Clinical Lab. Tests	Х		Х	Х				Х	Х	Х	Х		
(Hema., Chem.,													
Urinalysis)													
Prior and Concom. Meds.	X	X	X			X	X				X	X	X
Ocular Examinations***		X		X						X	X		
Modified Observer's			Х		Х			Х		Х			
Assess. of Alert./Sed.													
(MOAA/S)****													
Suicide Screening (C- SSRS)	X	X	X	X	X	X	X	X	X	X	X	X	X
Mood and Cognitive		X	X	X	X	X	X	X	X	X	X	X	X
Assessment (POMS)													
Clin. Admin. Diss. States			X		X			X		X			
Scale (CADSS)*****													
IV Drug Administration			X		X			X		X			
Blood Sample Coll. (PK)			X	X	X			X		X	X		
Check-in & Confinement		X	X	X	X		X	X	X	X			
Check-out*****						X					X		
Adverse Events			X	X	X	X		X	X	X	X	X	X
Outpatient Visit													
Phone Call												X	Х

Table 2: MAD schedule of assessments and procedures

An early termination visit will be scheduled on an ad hoc basis for any subject who withdraws from the study.

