6.5 On Treatment Population

All participants who completed all doses for their treatment group.

7. General Analysis Conventions

Analyses will be stratified by treatment assignment, dose groups, and sub studies (SAD, MAD, CSF):

- SAD
 - Cohorts 1 through 6 (2R,6R)-Hydroxynorketamine individually
 - Overall (2R,6R)-Hydroxynorketamine
 - Overall placebo
- MAD
 - Cohorts 1 through 2 (2R,6R)-Hydroxynorketamine individually
 - Overall (2R,6R)-Hydroxynorketamine
 - Overall placebo
- CSF
 - Cohort 1 (2R,6R)-Hydroxynorketamine individually
 - o Overall placebo

General statistical approaches are presented below.

All subjects in the Safety Population will be included in the safety analysis grouped by study, cohort, and treatment group. Statistical analysis of safety data will be descriptive.

Baseline is defined as the last non-missing assessment prior to dosing of study medication.

For continuous variables, summaries will include sample size, mean, median, 25th and 75th percentiles, standard deviation, minimum, and maximum. For categorical variables, the summaries will include frequencies and corresponding percentages. No inferential hypothesis testing will be performed. Repeat or unscheduled results will not be included in the summaries, but will be listed. Data from placebo subjects will be pooled for final presentations.

Missing data results will not be imputed. Data summaries and analyses (e.g. means) will be calculated using all available data. If the start day for an AE is missing, day of study drug administration will be used and AE will be considered treatment emergent. Neither month nor year will be imputed for AE.

Planned analyses are descriptive or exploratory. If presented, significance level and confidence intervals will use alpha of 0.05. No adjustments for multiple testing are planned.

Analyses will be performed using a UNIX server based installation of SAS Software, version 9.4 or newer.

8. Outcomes

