11.1 Final Analyses

All final, planned analyses identified in this SAP will be performed only after the last participant has completed the last study visit, safety period and had end of study assessments, and all relevant study data have been processed and integrated into the analysis database. In addition, no database may be locked or analyses completed until this SAP has been approved. Unblinding of treatment assignments will not occur until the data are locked.

12. Planned Analyses

The Safety Population will be used for all analyses unless otherwise specified.

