- 11. Specific Federal and International Regulations define classes of "Hazardous Materials" and "Dangerous Goods"
- 12. Baverel P, She D, Piper E; et al. A randomized, placebo-controlled, single ascendingdose study to assess the safety, tolerability, pharmacokinetics, and immunogenicity of

subcutaneous tralokinumab in Japanese healthy volunteers. *Drug Metab Pharmacokinet*. 2018;33(3):150-158.

13.2 Appendix 1: MOAA's:

Responsiveness scores of the Modified Observer's Assessment of Alertness/sedation Scale.

Response	Score
Responds readily to name spoken in normal tone	5
Lethargic response to name spoken in normal tone	4
Responds only after name is called loudly of repeatedly	3
Responds only after mild prodding or shaking	2
Does not respond to mild prodding or shaking	1
Does not respond to noxious stimulus	0

13.3 Appendix 2: POMS:

Abbreviated POMS (Revised Version)

Name:_____

Date:

Below is a list of words that describe feelings people have. Please CIRCLE THE NUMBER THAT BEST DESCRIBES HOW YOU FEEL RIGHT NOW.

	Not At All	A Little	Moderately	Quite a lot	Extremely
Tense	0	1	2	3	4
Angry	0	1	2	3	4
Worn Out	0	1	2	3	4
Unhappy	0	1	2	3	4
Proud	0	1	2	3	4
Lively	0	1	2	3	4
Confused	0	1	2	3	4
Sad	0	1	2	3	4
Active	0	1	2	3	4
On-edge	0	1	2	3	4
Grouchy	0	1	2	3	4
Ashamed	0	1	2	3	4
Energetic	0	1	2	3	4
Hopeless	0	1	2	3	4
Uneasy	0	1	2	3	4
Restless	0	1	2	3	4
Unable to concentrate	0	1	2	3	4
Fatigued	0	1	2	3	4
Competent	0	1	2	3	4
Annoyed	0	1	2	3	4
Discouraged	0	1	2	3	4
Resentful	0	1	2	3	4
Nervous	0	1	2	3	4

Miserable	0	1	2	3	4
-----------	---	---	---	---	---

	Not At All	A Little	Moderately	Quite a lot	Extremely
Confident	0	1	2	3	4
Bitter	0	1	2	3	4
Exhausted	0	1	2	3	4
Anxious	0	1	2	3	4
Helpless	0	1	2	3	4
Weary	0	1	2	3	4
Satisfied	0	1	2	3	4
Bewildered	0	1	2	3	4
Furious	0	1	2	3	4
Full of Pep	0	1	2	3	4
Worthless	0	1	2	3	4
Forgetful	0	1	2	3	4
Vigorous	0	1	2	3	4
Uncertain about things	0	1	2	3	4
Bushed	0	1	2	3	4
Embarrassed	0	1	2	3	4

Citation:

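### SAP 12.14 summarises MOAA/S only for scores other than 5, with no time point, counting unit or denominator, so its sedation statistics may not be comparable across doses

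*SAP*

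**What the plan says.** SAP section 12.14 has two sentences on MOAA/S. The first sets the summary: "Descriptive statistics for MOAAS total score not equal to 5 will be presented by treatment group and cohort". The second sets the listing: "A listing of MOASS data for all subjects as described above will be provided".

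The scale in SAP section 13.2 (Appendix 1) runs from 0 to 5. Score 5 reads "Responds readily to name spoken in normal tone"; every lower score is some loss of responsiveness.

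The general rules in SAP section 7 are: "For continuous variables, summaries will include sample size, mean, median, 25th and 75th percentiles, standard deviation, minimum, and maximum", and "For categorical variables, the summaries will include frequencies and corresponding percentages". The same section says "Missing data results will not be imputed". SAP section 12 adds: "The Safety Population will be used for all analyses unless otherwise specified".

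The assessment is repeated. For SAD, the footnote to Protocol Table 1 says "On Day 1, MOAA/S is performed preinfusion, during the infusion at approximately 20 min after start of infusion, 40 min after start of infusion", with a further one at about 1 hour. The footnote to Protocol Table 2 sets the same four assessments for each MAD dosing day (1, 4, 8 and 11). MOAA/S is not done in the CSF part (Protocol synopsis, Safety; Protocol 12.8), so the point concerns SAD and MAD only.

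The neighbouring scales are handled differently. SAP 12.11 (POMS) and 12.13 (CADSS) summarise all scores at baseline and the change at each assessment time point, and list the data for all subjects without qualification.

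**The concern.** The rule selects observations by the value of the outcome being described. Once the fully alert scores are dropped, a mean, median or quartile describes depth of sedation among those already sedated. It does not show how common sedation was. Doses that sedate different numbers of people are then compared on different and self-selected subsets.

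Three choices are left to whoever programs the table: which time points are shown and whether preinfusion scores count, whether the unit is a subject or a record, and what any percentage is taken over. The listing sentence, alone among these scales, refers back to the restricted description. It could therefore be read as listing only the scores other than 5.

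What is at stake is a plain reading of sedation by dose and against pooled placebo. Protocol 8.7 includes MOAA/S because of the drug's relationship to ketamine, and SAP 9.1 lists it among the primary endpoints.

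**Working it through.** The plan states no figure for this point, and no power or alpha calculation bears on it. The check is direct enumeration.

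**Inputs**
- Active subjects per cohort: 6, in both SAD and MAD (SAP section 10).
- MOAA/S assessments per SAD subject: 4, of which 3 are after the start of infusion (Protocol Table 1 footnote).
- MOAA/S assessments per MAD subject: 4 × 4 dosing days = 16, of which 3 × 4 = 12 are after the start of an infusion (Protocol Table 2 footnote).
- The score patterns in steps 2 and 3 are hypothetical. The documents give no expected sedation rate.

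**Step 1: records against subjects.** An active SAD cohort yields 6 × 4 = 24 records, 6 × 3 = 18 of them post-start. An active MAD cohort yields 6 × 16 = 96, with 6 × 12 = 72 post-start. If k post-start records differ from 5 and each subject has m post-start records, the number of distinct subjects lies between ceil(k/m) and min(6, k).

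| k | SAD (m = 3) | MAD (m = 12) |
|---|---|---|
| 3 | 1 to 3 | 1 to 3 |
| 6 | 2 to 6 | 1 to 6 |
| 12 | 4 to 6 | 1 to 6 |

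So a pooled n does not give the number of sedated subjects. If the table is by time point (and by dosing day in MAD), each subject contributes one record per cell, and n is the number with reduced alertness at that point.

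**Step 2: restricted mean against the whole cohort, one time point, six subjects.**

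| Cohort | Scores | n below 5 | Restricted mean | Mean of all six | Proportion below 5 |
|---|---|---|---|---|---|
| A | one 3, five 5 | 1 | 3/1 = 3.0 | (3 + 25)/6 = 4.67 | 1/6 = 16.7% |
| B | six 4 | 6 | 24/6 = 4.0 | 24/6 = 4.00 | 6/6 = 100% |
| C | one 4, five 5 | 1 | 4/1 = 4.0 | (4 + 25)/6 = 4.83 | 1/6 = 16.7% |

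On the restricted mean, A looks worse than B; on the all-subject mean and on the proportion, B is worse. The restricted medians (3 and 4) reverse in the same way. C and B have the same restricted mean although one subject is sedated in C and six in B. Only the n column separates them.

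**Step 3: denominator and listing.** Missing results are not imputed. If scores of 5 appear in neither table nor listing, a subject with no entry may have been alert or not assessed. With one subject below 5, the proportion is 1/6 = 16.7% if all six were assessed and 1/5 = 20.0% if one was missed. The restricted output would not show which applies.

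**The case against.** The strongest reply is that the SAP's general conventions already supply the count. A continuous summary includes sample size, so cohorts B and C above would show n = 6 and n = 1, and a reader who looks at n is not misled. MOAA/S is also a six-level ordinal scale with a verbal anchor for each level. A score other than 5 is then naturally read as a yes/no category, for which section 7 gives frequencies and percentages. The Safety Population and the planned 6 + 2 cohort sizes supply a denominator. A reader might infer that the table cannot show how many subjects were sedated at each dose. The documents do not support that: read by subject and time point, 12.14 gives the number.

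A reader might also infer that alert subjects will be left out of the listing. That is not established either. The sentence says all subjects, and SAP 12.5 promises listings behind every summary; the qualifying phrase only leaves the restriction open.

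On importance, SAP 9.1 is an unranked list of twelve items that includes concomitant medications. SAP 8.1 does not name MOAA/S among the primary outcome measures, and the analyses are descriptive. Clinically significant sedation would also be captured as an adverse event (SAP 12.6) and summarised by severity and dose (Protocol 13.1).

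All of this stands and limits the point. It does not remove it. The categorical reading is one of several that the wording allows, and 12.14 opens with the same words as the POMS and CADSS sections, which suggests a score summary. The safety-set denominator gives the number dosed, which need not be the number assessed at a time point. Printing n beside a restricted mean does not make that mean comparable between doses.

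**Conclusion.** The point holds as a restriction on the outcome combined with under-specification. Section 12.14 selects on the score and states no time point, unit or denominator. Restricted means and medians are not comparable across doses and can reverse their order (3.0 against 4.0 where 1/6 and 6/6 are sedated). The number of sedated subjects is recoverable only if subjects are counted by time point. If records are pooled, six post-start scores below 5 are compatible with 2 to 6 of 6 subjects in SAD and 1 to 6 in MAD. The listing may or may not cover scores of 5; if it does not, an alert subject cannot be told from a missing assessment.

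The ranges assume six active subjects dosed per cohort and every scheduled assessment done. The score patterns are illustrations and say nothing about how often sedation will occur. The data are collected under the protocol, so this is a free improvement to the reporting. It is not a flaw in the design or in data capture.

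**What to change.** Replace the two sentences of SAP 12.14 with:

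> Number and percentage (n/N, N = Safety Population subjects assessed) with MOAA/S below 5 at each scheduled time point (and each dosing day in MAD), preinfusion shown separately, and the distribution of each subject's lowest post-start score, by dose and pooled placebo within SAD and MAD. All MOAA/S scores, including 5, will be listed for all subjects.

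This fixes the unit, the time points and the denominator, and makes sedation comparable across doses and against placebo. The lowest-score distribution keeps the information on depth of sedation. The cost is the replaced SAP text, one revised table shell and confirmation that the listing is complete. No new data, visits or subjects are needed.

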- 11. Specific Federal and International Regulations define classes of "Hazardous Materials" and "Dangerous Goods"
- 12. Baverel P, She D, Piper E; et al. A randomized, placebo-controlled, single ascendingdose study to assess the safety, tolerability, pharmacokinetics, and immunogenicity of

subcutaneous tralokinumab in Japanese healthy volunteers. *Drug Metab Pharmacokinet*. 2018;33(3):150-158.

13.2 Appendix 1: MOAA's:

Responsiveness scores of the Modified Observer's Assessment of Alertness/sedation Scale.

Response	Score
Responds readily to name spoken in normal tone	5
Lethargic response to name spoken in normal tone	4
Responds only after name is called loudly of repeatedly	3
Responds only after mild prodding or shaking	2
Does not respond to mild prodding or shaking	1
Does not respond to noxious stimulus	0

13.3 Appendix 2: POMS:

Abbreviated POMS (Revised Version)

Name:_____

Date:

Below is a list of words that describe feelings people have. Please CIRCLE THE NUMBER THAT BEST DESCRIBES HOW YOU FEEL RIGHT NOW.

	Not At All	A Little	Moderately	Quite a lot	Extremely
Tense	0	1	2	3	4
Angry	0	1	2	3	4
Worn Out	0	1	2	3	4
Unhappy	0	1	2	3	4
Proud	0	1	2	3	4
Lively	0	1	2	3	4
Confused	0	1	2	3	4
Sad	0	1	2	3	4
Active	0	1	2	3	4
On-edge	0	1	2	3	4
Grouchy	0	1	2	3	4
Ashamed	0	1	2	3	4
Energetic	0	1	2	3	4
Hopeless	0	1	2	3	4
Uneasy	0	1	2	3	4
Restless	0	1	2	3	4
Unable to concentrate	0	1	2	3	4
Fatigued	0	1	2	3	4
Competent	0	1	2	3	4
Annoyed	0	1	2	3	4
Discouraged	0	1	2	3	4
Resentful	0	1	2	3	4
Nervous	0	1	2	3	4

Miserable	0	1	2	3	4
-----------	---	---	---	---	---

	Not At All	A Little	Moderately	Quite a lot	Extremely
Confident	0	1	2	3	4
Bitter	0	1	2	3	4
Exhausted	0	1	2	3	4
Anxious	0	1	2	3	4
Helpless	0	1	2	3	4
Weary	0	1	2	3	4
Satisfied	0	1	2	3	4
Bewildered	0	1	2	3	4
Furious	0	1	2	3	4
Full of Pep	0	1	2	3	4
Worthless	0	1	2	3	4
Forgetful	0	1	2	3	4
Vigorous	0	1	2	3	4
Uncertain about things	0	1	2	3	4
Bushed	0	1	2	3	4
Embarrassed	0	1	2	3	4

Citation:

Grove, J.R., & Prapavessis, H. (1992). Preliminary evidence for the reliability and validity of an abbreviated Profile of Mood States. *International Journal of Sport Psychology, 23*, 93-109.

> Copyright © 1993 J.R. Grove, PhD The University of Western Australia

*** SCORING KEY ***

Scores for the seven subscales in the abbreviated POMS are calculated by summing the numerical ratings for items that contribute to each subscale. The correspondence between items and subscales is shown below.

Item	Scale	Not At All	A Little	Moderate	Quite a lot	Extremely
Tense	TEN	0	1	2	3	4
Angry	ANG	0	1	2	3	4
Worn Out	FAT	0	1	2	3	4
Unhappy	DEP	0	1	2	3	4
Proud	ERA	0	1	2	3	4
Lively	VIG	0	1	2	3	4
Confused	CON	0	1	2	3	4
Sad	DEP	0	1	2	3	4
Active	VIG	0	1	2	3	4
On-edge	TEN	0	1	2	3	4
Grouchy	ANG	0	1	2	3	4
Ashamed	ERA	Reverse-	score this iter	m $[0 = 4, 1 =$	3, 2 = 2, 3 =	1, 4 = 0]
Energetic	VIG	0	1	2	3	4
Hopeless	DEP	0	1	2	3	4
Uneasy	TEN	0	1	2	3	4
Restless	TEN	0	1	2	3	4
Can't concentrate	CON	0	1	2	3	4
Fatigued	FAT	0	1	2	3	4
Competent	ERA	0	1	2	3	4
Annoyed	ANG	0	1	2	3	4
Discouraged	DEP	0	1	2	3	4
Resentful	ANG	0	1	2	3	4
Nervous	TEN	0	1	2	3	4
Miserable	DEP	0	1	2	3	4

Item	Scale	Not At All	A Little	Moderate	Quite a lot	Extremely	
Confident	ERA	0	1	2	3	4	
Bitter	ANG	0	1	2	3	4	
Exhausted	FAT	0	1	2	3	4	
Anxious	TEN	0	1	2	3	4	
Helpless	DEP	0	1	2	3	4	
Weary	FAT	0	1	2	3	4	
Satisfied	ERA	0	1	2	3	4	
Bewildered	CON	0	1	2	3	4	
Furious	ANG	0	1	2	3	4	
Full of Pep	VIG	0	1	2	3	4	
Worthless	DEP	0	1	2	3	4	
Forgetful	CON	0	1	2	3	4	
Vigorous	VIG	0	1	2	3	4	
Uncertain	CON	0	1	2	3	4	
Bushed	FAT	0	1	2	3	4	
Embarrassed	ERA	Reverse-score this item [0 = 4, 1 = 3, 2 = 2, 3 = 1, 4 = 0]					

TEN = Tension	Note that 2 of the items on the Esteem-related Affect (ERA) subscale are reverse-scored prior to being combined with the other items.				
ANG = Anger					

FAT = Fatigue	Total Mood Disturbance (TMD) is calculated					
DEP = Depression	by summing the totals for the negative subscales and then subtracting the totals for the positive subscales:					
ERA = Esteem-related Affect	TMD = [TEN+DEP+ANG+FAT+CON] –					
VIG = Vigour	[VIG+ERA]. A constant (e.g., 100) can be added to the TMD					
CON = Confusion	formula in order to eliminate negative scores.					

13.4 Appendix 3: C-CSSR:

COLUMBIA-SUICIDE SEVERITY RATING SCALE (C-SSRS) Baseline/Screening Version

Version 1/14/09

Posner, K.; Brent, D.; Lucas, C.; Gould, M.; Stanley, B.; Brown, G.; Fisher, P.; Zelazny, J.; Burke, A.; Oquendo, M.; Mann, J.

Disclaimer:

This scale is intended to be used by individuals who have received training in its administration. The questions contained in the Columbia-Suicide Severity Rating Scale are suggested probes. Ultimately, the determination of the presence of suicidal ideation or behavior depends on the judgment of the individual administering the scale.

Definitions of behavioral suicidal events in this scale are based on those used in The Columbia Suicide History Form, developed by [name] and [name], Conte Center for the Neuroscience of Mental Disorders (CCNMD), New York State Psychiatric Institute, [name]. (Oquendo M. A., Halberstam B. & Mann J. J., Risk factors for suicidal behavior: utility and limitations of research instruments. In M.B. First [Ed.] Standardized Evaluation in Clinical Practice, pp. 103 -130, 2003.)

For reprints of the C-SSRS contact [name]., New York State Psychiatric Institute, [name]; inquiries and training requirements contact [contact]

© 2008 The Research Foundation for Mental Hygiene, Inc

SUICIDAL IDEATION Ask questions 1 and 2. If both are negative, proceed to "Suicidal Behavior" section. If the answer	to				
Ask questions 1 and 2. If both are negative, proceed to "Suicidal Benavior" section. If the answer to question 2 is "yes", ask questions 3, 4 and 5. If the answer to question 1 and/or 2 is "yes", complete "Intensity of Ideation" section below.		Lifetime: Time He/She Felt Most Suicidal		Past Months	
1. Wish to be Dead					
Subject endorses thoughts about a wish to be dead or not alive anymore, or wish to fall asleep and not wake up. Have you wished you were dead or wished you could go to sleep and not wake up?	Yes		Yes	No	
If yes, describe:					
2. Non-Specific Active Suicidal Thoughts					
General non-specific thoughts of wanting to end one's life/commit suicide (e.g., "I've thought about killing myself") wit	hout Ye	s No	Yes	N	
thoughts of ways to kill oneself/associated methods, intent, or plan during the assessment period. Have you actually had any thoughts of killing yourself?					
If yes, describe:					
3. Active Suicidal Ideation with Any Methods (Not Plan) without Intent to Act Subject endorses thoughts of suicide and has thought of at least one method during the assessment period. This is diffe	erent than a Ye	i No	Yes	N	
specific plan with time, place or method details worked out (e.g. thought of method to kill self but not a specific plan).			_	_	
person who would say, "I thought about taking an overdose but I never made a specific plan as to when, where or how				Ľ	
actually do itand I would never go through with it."					
Have you been thinking about how you might do this?					
If yes, describe:					
4. Active Suicidal Ideation with Some Intent to Act, without Specific Plan					
Active suicidal thoughts of killing oneself and subject reports having some intent to act on such thoughts, as opposed to	o "I have Yes	No	Yes	N	
the thoughts but I definitely will not do anything about them."				Ľ	
Have you had these thoughts and had some intention of acting on them?					
If yes, describe:					
5. Active Suicidal Ideation with Specific Plan and Intent	Yee	Nia	Maa		
Thoughts of killing oneself with details of plan fully or partially worked out and subject has some intent to carry it out.	Yes	No	Yes	N	
Have you started to work out or worked out the details of how to kill yourself? Do you intend to carry out this plan?					
If yes, describe:					
INTENSITY OF IDEATION					
The following features should be rated with respect to the most severe type of ideation (i.e., 1-5 from above	re, with 1				
being the least severe and 5 being the most severe). Ask about time he/she was feeling the most suicidal.					
etime - Most Severe Ideation:		Vost		lost	
Type # (1-5) Description of Ideation	S	evere	Sev	vere	
Past X Months - Most Severe Ideation:					
Type # (1-5) Description of Ideation					

Frequency		
How many times have you had these thoughts?		
(1) Less than once a week (2) Once a week (3) 2-5 times in week	(4) Daily or almost daily (5) Many times each day	
Duration		
When you have the thoughts how long do they last?		
(1) Fleeting - few seconds or minutes	(4) 4-8 hours/most of day	
(2) Less than 1 hour/some of the time(3) 1-4 hours/a lot of time	(5) More than 8 hours/persistent or continuous	
Controllability		
Could/can you stop thinking about killing yourself or want	ing to die if you want to?	
(1) Easily able to control thoughts	(4) Can control thoughts with a lot of difficulty	
(2) Can control thoughts with little difficulty	(5) Unable to control thoughts	
(3) Can control thoughts with some difficulty	(0) Does not attempt to control thoughts	
Deterrents		
Are there things - anyone or anything (e.g., family, religion	n, pain of death) - that stopped you from wanting	
to die or acting on thoughts of committing suicide?		
$\left(1 ight)$ Deterrents definitely stopped you from attempting suicide	(4) Deterrents most likely did not stop you	
(2) Deterrents probably stopped you	(5) Deterrents definitely did not stop you	
(3) Uncertain that deterrents stopped you	(0) Does not apply	
Reasons for Ideation		
What sort of reasons did you have for thinking about wan	ting to die or killing yourself? Was it to end the pain	
or stop the way you were feeling (in other words you could	dn't go on living with this pain or how you were	
feeling) or was it to get attention, revenge or a reaction fr	om others? Or both?	
(1) Completely to get attention, revenge or a reaction from others	(4) Mostly to end or stop the pain (you couldn't go on	
(2) Mostly to get attention, revenge or a reaction from others	living with the pain or how you were feeling)	
(3) Equally to get attention, revenge or a reaction from others	(5) Completely to end or stop the pain (you couldn't go	
on and to end/stop the pain	living with the pain or how you were feeling)	
	(0) Does not apply	
2008 Research Foundation for Mental Hygiene, Inc.	-SSRS—Baseline/Screening (Version 1/14/09)	Page 1 of 2

SUICIDAL BEHAVIOR (Check all that apply, so long as these are separate events; must ask about all types)		Lifetime		t Yea	
Actual Attempt:	Yes	No	Yes	No	
A potentially self-injurious act committed with at least some wish to die, as a result of act. Behavior was in part thought of as method to kill					
oneself. Intent does not have to be 100%. If there is any intent/desire to die associated with the act, then it can be considered an actual					
suicide attempt. There does not have to be any injury or harm, just the potential for injury or harm. If person pulls trigger while gun					
is in mouth but gun is broken so no injury results, this is considered an attempt.					
Inferring Intent: Even if an individual denies intent/wish to die, it may be inferred clinically from the behavior or circumstances. For example, a highly lethal act that is clearly not an accident so no other intent but suicide can be inferred (e.g., gunshot to head, jumping from window of					
a high floor/story). Also, if someone denies intent to die, but they thought that what they did could be lethal, intent may be inferred.					
Have you made a suicide attempt?					
Have you done anything to harm yourself?	Tota	l # of	Tota	l # of	
Have you done anything dangerous where you could have died?	Atte	empts	Atte	mpts	
What did you do?					
Did youas a way to end your life?	-				
Did you want to die (even a little) when you?					
Were you trying to end your life when you?					
Or Did you think it was possible you could have died from?					
Or did you do it purely for other reasons / without ANY intention of killing yourself (like to relieve stress, feel					
better, get sympathy, or get something else to happen)? (Self-Injurious Behavior without suicidal intent)					
If yes, describe:	Yes	No	Yes	No	
Has subject engaged in Non-Suicidal Self-Injurious Behavior?					
Interrupted Attempt:	Yes	No	Yes	No	
When the person is interrupted (by an outside circumstance) from starting the potentially self-injurious act (if not for that, actual attempt would have occurred).					
Overdose: Person has pills in hand but is stopped from ingesting. Once they ingest any pills, this becomes an attempt rather than an interrupted					
attempt. Shooting: Person has gun pointed toward self, gun is taken away by someone else, or is somehow prevented from pulling trigger. Once					
they pull the trigger, even if the gun fails to fire, it is an attempt. Jumping: Person is poised to jump, is grabbed and taken down from ledge.					
Hanging: Person has noose around neck but has not yet started to hang - is stopped from doing so. Has there been a time when you started to do something to end your life but someone or something stopped you		Total # of		Total # of	
before you actually did anything?	inter	rupted	interr	upte	
If yes, describe:					
Aborted Attempt:	Yes	No	Yes	No	
When person begins to take steps toward making a suicide attempt, but stops themselves before they actually have engaged in any self-					
destructive behavior. Examples are similar to interrupted attempts, except that the individual stops him/herself, instead of being stopped by					
something else.	-		Tota	4.4	
Has there been a time when you started to do something to try to end your life but you stopped yourself before		ll # of orted	Tota abo	rted	
you actually did anything? If yes, describe:	abt	nieu	uso	·····	

Preparatory Acts or Behavior: Acts or preparation towards imminently making a suicide attempt. This can include anything beyond a verbalization or thought, such as assembling a specific method (e.g., buying pills, purchasing a gun) or preparing for one's death by suicide (e.g., giving things away, writing a suicide note).		Yes	No	Yes	No
Have you taken any steps towards making a suicide attempt or preparing to kill yourself (such as colle pills, getting a gun, giving valuables away or writing a suicide note)? If yes, describe:	cting				
Suicidal Behavior: Suicidal behavior was present during the assessment period?		Yes	No	Yes	No
Answer for Actual Attempts Only	Most Recent Attempt Date:	Most Let Attempt Date:		Initial/Fir Attempt Date:	rst
 Actual Lethality/Medical Damage: No physical damage or very minor physical damage (e.g., surface scratches). Minor physical damage (e.g., lethargic speech; first-degree burns; mild bleeding; sprains). Moderate physical damage; medical attention needed (e.g., conscious but sleepy, somewhat responsive; second-degree burns; bleeding of major vessel). Moderately severe physical damage; medical hospitalization and likely intensive care required (e.g., comatose with reflexes intact; third-degree burns less than 20% of body; extensive blood loss but can recover; major fractures). Severe physical damage; medical hospitalization with intensive care required (e.g., comatose without reflexes; third-degree burns over 20% of body; extensive blood loss with unstable vital signs; major damage to a vital area). Death 	Enter Code	Enter	Code	Enter (Code
Potential Lethality: Only Answer if Actual Lethality=0 Likely lethality of actual attempt if no medical damage (the following examples, while having no actual medical damage, had potential for very serious lethality: put gun in mouth and pulled the trigger but gun fails to fire so no medical damage; laying on train tracks with oncoming train but pulled away before run over). 0 = Behavior not likely to result in injury 1 = Behavior likely to result in injury but not likely to cause death 2 = Behavior likely to result in death despite available medical care	Enter Code	Enter	Code	Enter (Code
008 Research Foundation for Mental Hygiene, Inc. C-SSRS—Baseline/Screening (Version 1/14/09)				Page 2 o	of 2

13.5 Appendix 4: CADSS:

The Clinician Administered Dissociative States Scale (CADSS)

Name ID Date

Subjective Items:

1. Do things seem to be moving in slow motion?

0 = Not at all.

1= Mild, things seem slightly slowed down, but not very noticeable.

2= Moderate, things are moving about twice as slow as normally.

3= Severe, things are moving so slowly that they are barely moving.

4= Extreme, things are moving so slowly, I have the perception that everything has come to a stop, as if time is standing still.

2. Do things seem to be unreal to you, as if you are in a dream?

0 = Not at all.

1= Mild, things seem a little unreal, but I'm well aware of where I'm at.

2= Moderate, things seem dreamlike, although I know I am awake.

3= Severe, things seem very dreamlike, although I know that I am here, I have the feeling like I might be asleep.

4= Extreme, I feel like nothing is real, like I should pinch myself to wake up, or ask someone if this is a dream.

3. Do you have some experience that separates you from what is happening;

for instance, do you feel as if you are in a movie or a play, or as if you are a robot? 0= Not at all.

1= Mild, I feel a little bit separated from what is happening, but I am basically here.

2= Moderate, I feel somewhat separated from what is going on, or I feel as if I am in a movie or a play.

3= Severe, I feel extremely separated from what is happening, but I can understand what people are saying.

4= Extreme, I feel as if everyone around me is talking a foreign language, so that I cannot understand what they are saying, or I feel as if I am on the outside looking in, or like I am a robot or a machine.

4. Do you feel as if you are looking at things from outside of your body? 0= Not at all.

1= Mild, I feel somewhat disconnected from myself, but I am basically all together.

2= Moderate, I feel like I am just outside of my body, but not looking down upon myself from far above.

3= Severe, I feel like I am twenty feet or more away from my body, looking down from above.

4= Extreme, I feel as if I am hundreds of feet above myself, looking down at myself and everyone else here.

5. Do you feel as if you are watching the situation as an observer or a spectator? 0= Not at all. 1= Mild, I feel slightly detached from what is going on, but I am basically here.

2= Moderate, I feel somewhat removed as an observer or a spectator, but I am definitely in this room.

3= Severe, I feel very much as if I am an observer or a spectator, but I am still here in this room.

4= Extreme, I feel completely removed from what is happening, as if I am not a part of this experience in any way, but totally removed from what is happening, as an observer or a spectator.

6. Do you feel disconnected from your own body?

0 = Not at all.

1= Mild, I feel a little bit disconnected from myself, but I am basically all here.

2= Moderate, I feel somewhat detached from my own body, but I am basically all together.

3= Severe, I feel detached from my own body, but not far removed from my body, and I feel as if it is me there.

4= Extreme, I feel like I am completely out of my body, as if I am looking at my own body from a long way off, as if there is another person there.

7. Does your sense of your own body feel changed: for instance, does your own body feel unusually large or unusually small?

0= Not at all.

1= Mild, I have a vague feeling that something about my body has changed, but I can't say exactly what it is.

2= Moderate, I feel like my body has increased or decreased in size slightly, or that it feels somewhat as if it is not my body.

3= Severe, I feel as if my body has increased to twice its normal size, or decreased to twice its normal size, or I very much feel as if this is not my body.

4= Extreme, I feel as if my body has swelled up to at least ten times its normal size, or as if it is ten times as small, or as if my arms have become like toothpicks.

8. Do people seem motionless, dead, or mechanical?

0 = Not at all.

1= Mild, people seem a little bit more motionless, dead, or mechanical than would be normal.

2= Moderate, people seem to be at least twice as motionless or mechanical than would be normal.

3= Severe, people seem to be barely moving, or barely alive, or very mechanical.

4= Extreme, it's as if everyone were frozen or completely like machines.

9. Do objects look different than you would expect?

0 = Not at all.

1= Mild, things seem slightly different than normal, although it is barely perceptible.

2= Moderate, things are somewhat distorted, but I have no problems recognizing things around me.

3= Severe, things are much more distorted or unreal than normal, but I am able to recognize things in the room.

4= Extreme, like everything is distorted, not real, I feel like I cannot recognize anything, everything is alien or strange.

10. Do colors seem to be diminished in intensity?

0 = Not at all.

1= Mild, things seem slightly paler than usual if I think about it.

2= Moderate, colors are somewhat diminished, but still recognizable.

3= Severe, colors are extremely pale, in no way as vivid as they usually are.

4= Extreme, as if everything is in black and white, or all the colors have been washed out.

11. Do you see things as if you were in a tunnel, or looking through a wide angle photographic lens?

0 = Not at all.

1= Mild, I feel a little bit like I am looking through a tunnel, or a wide angle lens.

